9. STATISTICAL METHODOLOGY

9.1 General

Data listings will be provided for all data that is databased. Summary statistics and statistical analysis will only be presented for data where detailed in this SAP. For continuous data, summary statistics will include the arithmetic mean, arithmetic standard deviation, median, min, max and N; for log-normal data (e.g. the PK parameters: area under the concentration versus time curve [AUCs] and maximum observed drug concentration [C_{max}]) the geometric mean and geometric coefficient of variation (CV%) will also be presented. For categorical data, frequency count and percentages will be presented. Data listings will be provided for all subjects up to the point of withdrawal, with any subjects excluded from the relevant population highlighted. Summary statistics and statistical analyses will generally only be performed for subjects included in the relevant analysis population. For the calculation of summary statistics and statistical analysis, unrounded data will be used.

Data analysis will be performed using SAS® Version 9.4 or greater.

9.2 Demographics and Subject Disposition

Subject disposition will be listed. The demographic variables age, sex, race, ethnicity, body weight, height and body mass index will be summarized and listed. All other demographic variables will be listed only.

9.3 Pharmacokinetic Assessment

The PK parameter estimates will be determined using non-compartmental methods in validated software program, Phoenix WinNonlin (Certara, Version 8.1 or later):

Pharmacokinetics of LY3470845

Following oral administration of LY3478045 (alone or with atorvastatin) in Part A and Part B, plasma concentrations of LY3478045 will be used to determine the following PK parameters where possible.

Parameter	Units	Definition
AUC(0-∞)	ng.h/mL	Area under the concentration versus time curve from time zero to infinity (Part A, Part B on Day 1 and 14 only)
AUC(0-t _{last})	ng.h/mL	Area under the concentration versus time curve from time zero to time t, where t is the last time point with a measurable concentration (Part A, Part B on Day 1 only)
AUC(0-6)	ng.h/mL	Area under the concentration versus time curve from time zero to 6h postdose
AUC(0-24)	ng.h/mL	Area under the concentration versus time curve from time zero to 24h postdose
AUC(6-12)	ng.h/mL	Area under the concentration versus time curve from time 6h to 12h postdose
AUC(12-24)	ng.h/mL	Area under the concentration versus time curve from time 12h to 24h postdose
AUC _T	ng.h/mL	Area under the concentration versus time curve during the dosing interval (Part B only)
%AUC(t _{last} -∞)	%	Percentage of AUC that is due to extrapolation from the last measurable concentration to infinity (Part A, Part B on Day 1 only)
C _{max}	ng/mL	Maximum observed drug concentration
t _{max}	h	Time of maximum observed drug concentration
t _{1/2}	h	Half-life associated with the terminal rate constant (λ_z) in non-compartmental analysis
CL/F	L/h	Apparent total body clearance of drug calculated after extra-vascular administration
V _{ss} /F	L	Apparent volume of distribution at steady state after extra-vascular administration (Part A only)
V _z /F	L	Apparent volume of distribution during the terminal phase after extra-vascular administration
RA(AUC)	NA	Accumulation ratio based upon AUC(0-24)

$$RA(AUC) = \frac{AUC(Day\ 14)}{AUC(Day\ 1)}$$

RA (C_{max}) NA Accumulation ratio based upon C_{max}

$$RA (C_{max}) = \frac{C_{max}(\text{Day 14})}{C_{max}(\text{Day 1})}$$

NA: Not applicable

In addition, dose normalised parameters will be calculated for AUC(0-∞), AUC(0-t_{last}), AUC(0-24) and C_{max} by dividing the calculated parameter by the dose of LY3478045.

Following oral administration of LY3478045 in Part A, urine concentrations of LY3478045 will be used to determine the following PK parameters where possible.

Parameter	Units	Definition
A _e (t ₁ -t ₂)	mg	Amount excreted in urine, by interval and cumulative
f _e (t ₁ -t ₂)	%	Percentage of dose excreted in urine, by interval and cumulative
CL _R	L/h	Renal clearance

$$CL_R = \frac{A_e(0-\infty)}{AUC(0-\infty)}$$

Pharmacokinetics of CCI

Following oral administration of CCI with either LY3478045 or placebo, plasma concentrations of CCI will be used to determine the following PK parameters where possible.

Parameter	Units	Definition
AUC(0-∞)	ng.h/mL	Area under the concentration versus time curve from time zero to infinity
AUC(0-t _{last})	ng.h/mL	Area under the concentration versus time curve from time zero to time t, where t is the last time point with a measurable concentration
%AUC(t _{last} -∞)	%	Percentage of AUC that is due to extrapolation from the last measurable concentration to infinity
C _{max}	ng/mL	Maximum observed drug concentration
t _{max}	h	Time of maximum observed drug concentration
t _{1/2}	h	Half-life associated with the terminal rate constant (λ_z) in non-compartmental analysis
CL/F	L/h	Apparent total body clearance of drug calculated after extra-vascular administration (atorvastatin only)
V _{ss} /F	L	Apparent volume of distribution at steady state after extra-vascular administration (atorvastatin only)
V _z /F	L	Apparent volume of distribution during the terminal phase after extra-vascular administration (atorvastatin only)
MR(AUC)	NA	Metabolite ratio based upon AUC(0-∞) (metabolites only)
MR (C _{max})	NA	Metabolite ratio based upon C _{max} (metabolites only)

NA: Not applicable

Pharmacokinetics of Fructose for Pharmacodynamic Evaluation

Following administration of a fructose beverage the following parameter will be calculated.

Parameter	Units	Definition
AUC(0-6)	ng.h/mL	Area under the concentration versus time curve from time zero to 6h postdose
AUC(0-24)	ng.h/mL	Area under the concentration versus time curve from time zero to 24h postdose
AUC(6-12)	ng.h/mL	Area under the concentration versus time curve from time 6h to 12h postdose
AUC(12-24)	ng.h/mL	Area under the concentration versus time curve from time 12h to 24h postdose

Pharmacokinetics of CCI for Pharmacodynamic Evaluation

The following PK parameters will be calculated for CCI

Parameter	Units	Definition
AUC(0-t _{last})	ng.h/mL	Area under the concentration versus time curve from time zero to time t, where t is the last time point with a measurable concentration
AUC(0-24)	ng.h/mL	Area under the concentration versus time curve from time zero to 24 hours postdose
C _{max}	ng/mL	Maximum observed drug concentration
C _{predose}	ng/mL	Predose observed drug concentration
t _{max}	h	Time of maximum observed drug concentration

Additional PK parameters may be calculated where appropriate.

The software and version used for the final analysis will be specified in the clinical study report. Any exceptions or special handling of data will be clearly documented within the final study report.

Plasma PK analysis will, where possible, be carried out using actual postdose times recorded in the raw data.

Interim plasma PK analysis will be performed by Lilly for the decision regarding dose escalation.

Urine PK analysis will be calculated using nominal sample collection times

Formatting of tables, figures and abbreviations will follow the Eli Lilly Global PK/PD/TS Tool: NON-COMPARTMENTAL PHARMACOKINETIC STYLE GUIDE. The version of the tool effective at the time of PK analysis will be followed.

General PK Parameter Rules

- Actual sampling times will be used in the final analyses of individual PK parameters, except for non-bolus pre-dose sampling times which will be set to zero.
- C_{\max} and t_{\max} will be reported from observed values. If C_{\max} occurs at more than one time point, t_{\max} will be assigned to the first occurrence of C_{\max} .
- AUC parameters will be calculated using a combination of the linear and logarithmic trapezoidal methods (linear-log trapezoidal rule). The linear trapezoidal method will be applied up to t_{\max} and then the logarithmic trapezoidal method will be used after t_{\max} . The minimum requirement for the calculation of AUC will be the inclusion of at least three consecutive plasma concentrations above the lower limit of quantification (LLOQ), with at least one of these concentrations following C_{\max} .
- AUC($0-\infty$) values where the percentage of the total area extrapolated is more than 20% will be flagged. Any AUC($0-\infty$) value excluded from summary statistics will be noted in the footnote of the summary table. If AUC($0-\infty$) cannot be determined for all subjects an alternative AUC measure, such as AUC to a fixed time point, may be used in the assessment exposure between dose groups and metabolite ratios.
- Half-life ($t_{1/2}$) will be calculated, when appropriate, based on the apparent terminal log-linear portion of the concentration-time curve. The start of the terminal elimination phase for each subject will be defined by visual inspection and generally will be the first point at which there is no systematic deviation from the log-linear decline in plasma concentrations. Half-life will only be calculated when a reliable estimate for this parameter can be obtained comprising of at least 3 data points. If $t_{1/2}$ is estimated over a time window of less than 2 half-lives, the values will be flagged in the data listings. Any $t_{1/2}$ value excluded from summary statistics will be documented in the footnote of the summary table.
- A uniform weighting scheme will be used in the regression analysis of the terminal log-linear portion of the concentration-time curve.
- The parameters based on the last predicted quantifiable drug concentration (C_{last}) will be reported.

Individual PK Parameter Rules

- Only quantifiable concentrations will be used to calculate PK parameters with the exception of special handling of certain concentrations reported below the lower limit of quantitation (BQL). Plasma concentrations reported as BQL will be set to a value of zero when all of the following conditions are met:

- The compound is non-endogenous.
- The samples are from the initial dose period for a subject or from a subsequent dose period following a suitable wash-out period.
- The time points occur before the first quantifiable concentration.
- All other BQL concentrations that do not meet the above criteria will be set to missing.
- Also, where two or more consecutive concentrations are BQL towards the end of a profile, the profile will be deemed to have terminated and therefore any further quantifiable concentrations will be set to missing for the calculation of the PK parameters unless it is considered to be a true characteristic of the profile of the drug.
- Urine concentrations reported as BQL will be set to a value of zero.

Individual Concentration vs. Time Profiles

- Individual concentrations will be plotted utilizing actual sampling times.
- The terminal point selections will be indicated on a semi-logarithmic plot.

Average Concentration vs. Time Profiles

- The average concentration profiles will be graphed using scheduled (nominal) sampling times.
- The average concentration profiles will be graphed using arithmetic average concentrations.
- The pre-dose average concentration for single-dose data from non-endogenous compounds will be set to zero. Otherwise, only quantifiable concentrations will be used to calculate average concentrations.
- Concentrations at a sampling time exceeding the sampling time window specified in the protocol, or $\pm 10\%$, will be excluded from the average concentration profiles.
- Concentrations excluded from the mean calculation will be documented in the final study report.
- A concentration average will be plotted for a given sampling time only if 2/3 of the individual data at the time point have quantifiable measurements that are within the sampling time window specified in the protocol or $\pm 10\%$. An average concentration estimated with less than 2/3 but more than 3 data points may be displayed on the mean concentration plot if determined to be appropriate and will be documented within the final study report.

Treatment of Outliers during Pharmacokinetic Analysis

Application of this procedure to all PK analyses is not a requirement. Rather, this procedure provides justification for exclusion of data when scientifically appropriate. This procedure describes the methodology for identifying an individual value as an outlier for potential exclusion, but does not require that the value be excluded from analysis. The following methodology will not be used to exclude complete profiles from analysis.

Data within an Individual Profile

A value within an individual profile may be excluded from analysis if any of the following criteria are met:

- For PK profiles during single dosing of non-endogenous compounds, the concentration in a pre-dose sample is quantifiable.
- For any questionable datum that does not satisfy the above criteria, the profile will be evaluated and results reported with and without the suspected datum.

Data between Individual Profiles

1. If $n < 6$, then the dataset is too small to conduct a reliable range test. Data will be analyzed with and without the atypical value, and both sets of results will be reported.
2. If $n \geq 6$, then an objective outlier test will be used to compare the atypical value to other values included in that calculation:
 - a. Transform all values in the calculation to the logarithmic domain.
 - b. Find the most extreme value from the arithmetic mean of the log transformed values and exclude that value from the dataset.
 - c. Calculate the lower and upper bounds of the range defined by the arithmetic mean $\pm 3 \times \text{SD}$ of the remaining log-transformed values.
 - d. If the extreme value is within the range of arithmetic mean $\pm 3 \times \text{SD}$, then it is not an outlier and will be retained in the dataset.
 - e. If the extreme value is outside the range of arithmetic mean $\pm 3 \times \text{SD}$, then it is an outlier and will be excluded from analysis.

If the remaining dataset contains another atypical datum suspected to be an outlier and $n \geq 6$ following the exclusion, then repeat step 2 above. This evaluation may be repeated as many times as necessary, excluding only one suspected outlier in each iteration, until all data remaining in the dataset fall within the range of arithmetic mean $\pm 3 \times \text{SD}$ of the log-transformed values.

Reporting of Excluded Values

Individual values excluded as outliers will be documented in the final report. Approval of the final report will connote approval of the exclusion.

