9.6. Pharmacodynamics

Fructose Tolerance Test: Three meals (breakfast, lunch, and dinner) will be served at approximately 20 minutes, 6 hours, and 12 hours after dose with low fructose content. A beverage containing mixture of fructose and glucose CCI in approximately 300 to 500 mL of non-caloric solution will be served with each of the 3 meals on Day 1 in Part A (SAD) and Days 1 and 14 in Part B (MAD). The beverage should be served after a portion of the meal has been consumed. The meals should start at the defined time (20 minutes, 6 hours, and 12 hours postdose) Blood samples for the analysis of fructose will be collected into appropriately labeled tubes containing ethylene diamine tetra acetic acid at the time points specified in the Schedule of Activities (Section 2). Sample handling and shipment to the central laboratory will occur per instructions given to the study site.

The samples will be stored for up to a maximum of 1 year after the last subject visit for the study at a facility selected by the sponsor.

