9.4.3 Fructose Tolerance Test

Fructose Tolerance Test (FTT): Three meals (breakfast, lunch, and dinner) will be served at approximately 20 minutes, 6 hours, and 12 hours after dose with low fructose content. A beverage containing mixture of fructose CCI CCI in approximately 300 to 500 mL of non-caloric solution) will be served with each of the

3 meals on Day 1 in Part A, and Days 1 and 14 in Part B. AUC(0-24), AUC(0-6), AUC(6-12), and AUC(12-24) for FTT will be calculated using trapezoid methods.

In Part A, the AUC(0-24), AUC(0-6), AUC(6-12), and AUC(12-24) from the FTT will be log-transformed prior to analysis. A linear fixed effects model will be fitted to the fructose data. The model will include Treatment as a fixed effect. The difference in least-square treatment means (LY3478045 – Placebo) along with the 90% CIs will be back-transformed to produce the ratio of geometric means and the CIs comparing LY3478045 to Placebo.

Example of SAS code as follows:

```
proc mixed data=xxx;
class treatment;
model log_AUC = treatment /residual ddfm=kr;
lsmeans treatment / cl pdiff alpha=0.1;
ods output lsmeans=lsm diff=estims;
run;
```

In Part B, the AUC(0-24), AUC(0-6), AUC(6-12), and AUC(12-24) from the FTT will be log-transformed prior to analysis. A linear mixed effects model will be fitted to the data. The model will include treatment, day and the interaction between treatment and day as fixed effects and subject as a random effect. The difference in least-square treatment means (LY3478045 – Placebo) along with the 90% CIs will be back-transformed to produce the ratio of geometric means and the CIs comparing LY3478045 to Placebo. Similar comparisons will be calculated between Day 14 and Day 1 for LY3478045.

Example of SAS code as follows:

```
proc mixed data=xxx;
class treatment day subject;
model log_AUC = treatment|day /residual ddfm=kr;
random subject;
lsmeans treatment*day / cl pdiff alpha=0.1;
ods output lsmeans=lsm diff=estims;
run;
```

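### SAP 9.3's linear-to-tmax, log-after AUC rule does not suit a fructose profile with three challenges: a meal period's AUC depends on which meal gave the day's peak

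*SAP*

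**What the plan says.** SAP 9.3 lists four fructose areas under the line "Following administration of a fructose beverage the following parameter will be calculated": AUC(0-6), AUC(6-12), AUC(12-24) and AUC(0-24). The General PK Parameter Rules in the same section then state: "AUC parameters will be calculated using a combination of the linear and logarithmic trapezoidal methods (linear-log trapezoidal rule"). The switch point is tmax: "The linear trapezoidal method will be applied up to" tmax, "and then the logarithmic trapezoidal method will be used after" it. If the maximum occurs more than once, tmax "will be assigned to the first occurrence of" Cmax, so each profile has exactly one. The rule does not exempt fructose and does not define tmax by meal.

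Protocol 9.6 sets three challenges: "Three meals (breakfast, lunch, and dinner) will be served at approximately 20 minutes, 6 hours, and 12 hours after dose", with the fructose beverage at each meal, on Day 1 in Part A and on Days 1 and 14 in Part B. SAP 9.4.3 repeats this schedule and adds only "and AUC(12-24) for FTT will be calculated using trapezoid methods". Protocol 10.3.3.1 is equally general. It also names the fructose tolerance test as the main PD measure, and Protocol Table GZKA.1 lists fructose AUC(0-24) as the exploratory PD endpoint.

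**The concern.** A linear-to-tmax, log-after rule assumes one rise followed by one decline. Fructose here rises and falls three times. Two consequences follow from the text alone:

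- The method applied within a meal period is set by where the day's highest value lies, which may be in another period.
- If that value follows breakfast, the lunch and dinner rises are log-integrated. If it follows dinner, the breakfast and lunch falls are linear-integrated.

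SAP 9.4.3 analyses all four areas as ratios to placebo and, in Part B, also compares Day 14 with Day 1. A subject whose peak moves from one meal to another between those days would be integrated differently on each day. Cohorts have six active and two placebo subjects, so peak positions need not balance between groups. Protocol 5.5 uses serum fructose in Part A to describe target engagement by dose and to refine the predicted efficacious dose, so the individual and period values have a use beyond the formal comparison.

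**Working it through.** **1. Inputs.** From the documents: the rule and tmax definition (SAP 9.3); challenges at about 20 min, 6 h and 12 h (Protocol 9.6, SAP 9.4.3); 13 PD samples in Part A and 26 in Part B (Protocol Appendix 5), which is 13 per test day if split evenly. The plan gives no figure on this point, so there is none to reproduce. The sampling times are redacted, and the documents give no fructose baseline, amplitude or kinetics. Everything on those is an assumption.

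**2. One interval.** With r = C2/C1:

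- linear area = (C1 + C2)/2 × Δt
- log area = (C2 − C1)/ln(C2/C1) × Δt
- log/linear = [(r − 1)/ln r] / [(r + 1)/2]

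| r | calculation | log/linear |
|---|---|---|
| 2 | (1/0.693)/1.5 | 0.962 |
| 5 | (4/1.609)/3 | 0.828 |
| 10 | (9/2.303)/5.5 | 0.711 |
| 20 | (19/2.996)/10.5 | 0.604 |

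The ratio is the same for r and 1/r, so falls show the same gap. The log rule suits an exponential fall, which the linear rule overstates. It does not suit an absorption rise, which it understates.

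**3. One meal period, identical samples.** Assumed fast profile: absorption 2.5 per h, elimination 1.2 per h, rise 10 times a baseline of 1. Samples at 6, 6.75, 7.5, 9 and 12 h are 1.04, 10.61, 6.38, 2.01 and 1.03. If the day's peak follows breakfast, all four intervals lie after tmax (log). If it follows dinner, all four lie before it (linear).

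| Interval (h) | Linear | Log |
|---|---|---|
| 6 to 6.75 | 4.369 | 3.090 |
| 6.75 to 7.5 | 6.371 | 6.237 |
| 7.5 to 9 | 6.292 | 5.675 |
| 9 to 12 | 4.560 | 4.397 |
| AUC(6-12) | 21.59 | 19.40 |

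21.59/19.40 = 1.113: the same data give an AUC(6-12) 11% larger with the peak at dinner. Linear-up/log-down gives 4.369 + 6.237 + 5.675 + 4.397 = 20.68 wherever the day's peak lies. The fine-grid area is 22.42, so sparse sampling matters too. For an assumed slow profile (absorption 1.5 per h, elimination 0.35 per h) the two values are 50.32 and 48.52, a ratio of 1.037.

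**4. Range.** With two assumed 13-point grids, absorption 2 per h, elimination 0.12 to 0.9 per h and 30% variation per meal, AUC(6-12) is about 1% to 18% larger with tmax at dinner than at breakfast. A second set of assumptions (equal pulses, rises of 5, 10 and 20 times baseline) gave breakfast/dinner ratios of 0.975 to 0.833. Inverted, these are 1/0.975 = 1.026 to 1/0.833 = 1.20, or 2.6% to 20% larger. In that set AUC(0-24) moved by about 1% to 10%. The largest gaps come with fast elimination and a low baseline.

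**5. Does it reach the drug/placebo ratio?** Same model as the first set in step 4, with placebo elimination 0.9 per h, drug 0.6 down to 0.12 per h, and baseline 0.02 or 0.1 of the mean pulse amplitude scale. Entries are the estimated geometric mean ratio divided by the fine-grid true ratio.

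| | SAP rule | Linear-up/log-down | Largest difference in one scenario |
|---|---|---|---|
| AUC(0-24) | 0.978 to 1.074 | 0.980 to 1.063 | about 1.3 points |
| AUC(6-12) | 1.005 to 1.146 | 1.003 to 1.127 | about 2.3 points |

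True AUC(0-24) ratios ran from 1.3 to 5.7. The share of subjects peaking at dinner rose from 31-39% at the fastest elimination to 75-78% at the slowest. Most of the error in the ratio is sparse sampling, common to both rules. Neither rule was always closer: for AUC(6-12) on one grid with low baseline, the SAP rule gave 1.050 and linear-up/log-down 1.056.

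**The case against.** The strongest reply is that SAP 9.4.3 is the section specific to fructose and can be read as governing over a general bullet. The fructose table lists neither Cmax nor tmax, unlike the tables for the other analytes, so the switch point is not a planned fructose parameter. SAP 9.3 also allows special handling if it is documented in the report. The sponsor may therefore intend another variant. That possibility stands, but it does not remove the point. The wording in 9.4.3 covers the linear-log rule as well as any other, and the only variant actually stated is the tmax-based one. On either reading the variant for fructose has to be written down.

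The second reply is about consequence, and most of it stands. A reader might infer that slower fructose clearance on LY3478045 moves the peak toward dinner, so that the integration method differs systematically by arm and biases the comparison with placebo. The peak does move in simulation, but the ratio barely does, and the documents give no fructose kinetics or sampling times that would support a larger effect. A reader might also take the 40% shortfall for a 20-fold rise as an error in the endpoint. It is the gap on one interval for an arbitrary fold-rise, and no fructose AUC consists of one such interval.

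The choice of replacement is partly preference. All-linear integration would also remove the dependence on tmax. It was usually closer to the truth for AUC(6-12), though further from it for AUC(0-24) on one grid at slow elimination.

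**Conclusion.** The point holds as a defect of specification. As written, the rule makes a meal period's fructose AUC depend on data outside that period, and this follows from the text without any simulation. The size does rest on assumed kinetics, baselines and sampling times: roughly 1% to 18% for AUC(6-12) between a dinner and a breakfast peak, reaching 20% in the most extreme alternative profile. It is mainly an avoidable subject- and period-level artefact. Against linear-up/log-down, the drug/placebo ratio differs by about 1 point for AUC(0-24) and about 2 points for AUC(6-12), so a material treatment bias is not shown. The endpoint is exploratory and the primary safety conclusions are untouched, so this is a minor improvement.

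**What to change.** In SAP 9.3 and 9.4.3, exempt the fructose AUCs from the tmax-based switch and state one interval-by-interval rule for all subjects and all test days. Suitable wording: fructose AUCs are calculated by linear-up/log-down, with the linear rule on every rising or flat interval and the log rule on every falling interval. If the sponsor prefers all-linear integration, or already intends it, stating that would equally remove the dependence on tmax. Keep the present rule for LY3478045 and atorvastatin.

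The cost is one sentence in the SAP and one software setting, with no new samples or data. Neither alternative corrects the error from sparse sampling, and the fix should not be presented as doing so.

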3.2. Background

3.2.1. Nonalcoholic Steatohepatitis

Sugar consumption has significantly increased over the several decades; the per capita consumption of dietary fructose has increased 100-fold and fructose now accounts for approximately 10% of calorie intake in the United States (Bray et al. 2004; Tappy and Mittendorfer 2012). Furthermore, the polyol pathway, which converts glucose into fructose, is active in tissues including the liver, heart, and kidney. Activity of the polyol pathway is increased in metabolic disease conditions resulting in higher levels of endogenous fructose generated from glucose (Lanaspa et al. 2013; Andres-Hernando et al. 2019).

While modest amount of fructose found in fruits and vegetables is not of concern, the increased intake of sucrose (50% glucose/50% fructose) and high fructose corn syrup (55% to 90% fructose) is considered to be a cause for metabolic disease and complications including NAFLD/NASH.

Nonalcoholic steatohepatitis is the progressive stage of NAFLD, characterized histologically by the presence of steatosis, lobular inflammation, and hepatocyte injury (ballooning), with or without fibrosis (Chalasani et al. 2018).

Nonalcoholic steatohepatitis is currently the third most common cause of hepatocellular carcinoma (Chalasani et al. 2018) and NASH is expected to become the leading cause of liver transplantation in the future (Charlton et al. 2011).

Patients with NASH with fibrosis are at a higher risk of adverse outcomes, including liver cirrhosis, liver-related mortality, and cardiovascular (CV) mortality (Angulo et al. 2015). There is a high unmet medical need for safe and effective pharmacological treatments for NASH, as no approved therapies are currently available (Younossi et al. 2018).

3.2.2. *Ketohexokinase*

Ketohexokinase (also known as fructokinase) is the enzyme responsible for the first step in fructose metabolism (phosphorylation of fructose to fructose 1-phosphate).

As fructose (exogenous or endogenous), per se, is biologically inactive, metabolism by KHK is required to elicit negative metabolic phenotype(s) associated with fructose intake, including NAFLD/NASH and insulin resistance. Excessive fructose flux through KHK causes pro-lipogenic and inflammatory profiles in the liver where KHK is abundantly expressed and is the primary site of fructose metabolism (Hannou et al. 2018).

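### SAP 9.3 deletes every below-limit plasma fructose value, a rule that does not fit a three-drink profile; if such values occur, the LY3478045/placebo fructose AUC ratio can be biased in either direction

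*SAP*

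**What the plan says.** SAP 9.3 (Individual PK Parameter Rules) states that a plasma BQL value "will be set to a value of zero when all of the following conditions are met". The conditions are:

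1. "The compound is non-endogenous".
2. The sample comes from the initial dose period, or from a later period after washout.
3. "The time points occur before the first quantifiable concentration".

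Everything else falls under "All other BQL concentrations that do not meet the above criteria will be set to missing". A further rule ends the profile when two or more consecutive values towards its end are BQL and drops later quantifiable values, unless they are judged a true feature of the drug's profile. An AUC needs at least three consecutive quantifiable values, at least one of them after Cmax. For mean profiles, apart from single-dose predose values of non-endogenous compounds, "Otherwise, only quantifiable concentrations will be used to calculate average concentrations".

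Fructose belongs to the same section, under the title "Pharmacokinetics of Fructose for Pharmacodynamic Evaluation": "Following administration of a fructose beverage the following parameter will be calculated", followed by AUC(0-6), AUC(0-24), AUC(6-12) and AUC(12-24). Protocol 3.2.1 treats fructose as a compound the body makes, with metabolic disease "resulting in higher levels of endogenous fructose generated from glucose". SAP 9.4.3 describes drinks at about 20 minutes, 6 h and 12 h and a log-scale LY3478045/placebo comparison with 90% confidence intervals. It has no BQL rule, and SAP 13.2 (Missing Data) adds none.

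**The concern.** The rule suits a single-dose drug curve, where a BQL value marks the start or the end. A fructose curve with three drinks has troughs inside it, and they are part of the response. Three things can happen to BQL values:

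- **Between drinks.** The value comes after the first quantifiable one, so it fails condition 3. It is deleted, and the AUC is drawn from one peak's decline to the next peak.
- **Predose.** The value fails condition 1 because fructose is endogenous. It is deleted, and the curve loses its start.
- **Tail.** The value is deleted and the curve stops early. The termination rule may remove more.

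Protocol 3.2.2 says loss of ketohexokinase function raises the serum fructose excursion, so low values are more likely on placebo. The deletions would then depend on the effect being estimated.

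Fructose AUC(0-24) is exploratory (Protocol Table GZKA.1), but it is the primary PD measure (Protocol 10.3.3.1). Protocol 5.5 uses it to define target engagement at each dose and to refine the predicted efficacious dose. Part A compares all doses with one placebo group (SAP 6) of 2 subjects per cohort, at most 5 × 2 = 10. An error in that group enters every dose's ratio.

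**Working it through.** The plan states no figure to reproduce. It gives no fructose LLOQ, fasting level or trough level, and the sampling times are redacted (Protocol Appendix 5 implies 13 samples per test day). What follows shows mechanism and scale under assumptions; it is not a forecast.

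**Assumed inputs**
- Samples at 0, 0.75, 1.5, 3, 4, 6, 6.75, 8, 10, 12, 13, 16 and 24 h; drinks at d = 0.33, 6 and 12 h.
- C(t) = b + Σ A·ka/(ka − ke)·[exp(−ke(t − d)) − exp(−ka(t − d))], summed over drinks already taken, with ka = 2 per h.
- Placebo: A = 100, ke = 1.2 per h, b = 1. LY3478045, moderate effect: A = 150, ke = 0.6 per h, b = 2.
- No noise; linear trapezoid; linear interpolation at window boundaries. The placebo peak is 46.97 units.

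**All values known.** AUC(0-24) is 836.1 on LY3478045 and 287.8 on placebo: 836.1/287.8 = 2.91.

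**One window in full: AUC(6-12), LLOQ 10% of peak = 4.70**
- Placebo at 6, 6.75, 8, 10, 12 h: 1.27, 46.97, 19.13, 2.98, 1.19. Area = 18.09 + 41.31 + 22.11 + 4.17 = 85.7.
- LY3478045 at the same times: 9.13, 95.37, 64.77, 22.02, 8.05. Area = 39.19 + 100.09 + 86.79 + 30.07 = 256.1. Ratio 256.1/85.7 = 2.99.
- Under the rule, placebo loses 4, 6, 10 and 12 h. Bridging from 3 h (9.95) to 6.75 h puts 9.95 + (3/3.75)·37.02 = 39.57 at 6 h. Bridging from 8 h to 13 h (42.52) puts 19.13 + (4/5)·23.39 = 37.84 at 12 h.
- Placebo area becomes 32.45 + 41.31 + 113.94 = 187.7. Ratio 256.1/187.7 = 1.36.

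**AUC(0-24) ratio, known-value reference 2.91.** The third column deletes only between-drink values; the last two substitute all BQL values.

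| LLOQ, % of placebo peak (units) | Between-drink samples lost | Deleted | LLOQ/2 | Zero |
|---|---|---|---|---|
| 2% (0.94) | none | 2.91 | 2.91 | 2.91 |
| 5% (2.35) | placebo 6, 12 h | 836.1/376.7 = 2.22 | 2.88 | 2.95 |
| 10% (4.70) | placebo 4, 6, 10, 12 h | 836.1/470.3 = 1.78 | 2.89 | 3.28 |
| 20% (9.39) | placebo as above; LY 6, 12 h | 1021.4/470.3 = 2.17 | 2.55 | 3.19 |

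The linear-log rule behaves alike: 3.09 falls to 2.36 at 5% and 1.74 at 10%. With a stronger assumed effect (A = 200, ke = 0.35 per h, b = 4; linear) 6.49 falls to 4.96 and 3.97.

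**The opposite direction**
- *Tail loss, LLOQ 10%.* Placebo ends at 13 h and LY3478045, BQL at 24 h, ends at 16 h. AUC(12-24) is 224.7/40.2 = 5.59, against 3.03 with all values known.
- *Termination applied at 10 to 12 h.* If placebo ends at 8 h with its earlier values intact, AUC(0-24) is 836.1/155.6 = 5.37, against 2.91.
- *All BQL values deleted, LLOQ 10%, nothing extrapolated.* The effects partly offset: 710.5/369.3 = 1.92.

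**The case against.** A reader might infer that the fructose ratio is distorted and pulled towards 1. The documents do not support that. Nothing in them shows that any sample will be BQL. In the illustration no between-drink value is lost unless the LLOQ exceeds the assumed placebo fasting level of 1 unit, and no text suggests such an assay. The Amendment (c) rationale in Protocol Appendix 7 says fructose analysis was confirmed as robust and sufficient; that does not give an LLOQ, but it lends the worry no support. The direction is not fixed either, as the tail and termination results show.

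A reader might also blame the endogenous condition for the bridging. It is not the cause: between-drink values fail condition 3 whatever the compound. Condition 1 matters only for predose or early values.

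The SAP has safeguards. The termination rule has an exception. A mean is normally plotted only when two thirds of values at a time point are quantifiable. Special handling and excluded concentrations are to be documented, and all databased data are listed. These make the problem visible and limit it in the mean plots. They do not stop deletion inside the AUCs, and the termination exception is a judgement worded for a drug, not a dietary challenge.

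Dose escalation rests primarily on safety and tolerability (Protocol 7.4), and the endpoint is exploratory with unadjusted p-values. That lowers the priority. LLOQ/2 is also only a convention: it gave 2.55 instead of 2.91 at the highest LLOQ tried. That stands, and it is why a sensitivity analysis is needed.

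**Conclusion.** The point holds conditionally. As written, the SAP deletes every BQL plasma fructose value, and no fructose-specific text overrides this. It is a stated rule that does not fit the curve, not merely an omitted detail. If BQL values occur, they are more likely on placebo, and the LY3478045/placebo AUC ratios would be biased: towards 1 by bridging, possibly away from 1 by tail loss or termination. Some placebo profiles might also fail the three-consecutive-values minimum and yield no AUC.

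The size is unknown. It is nil if all samples are quantifiable. Under the assumed moderate-effect profiles, between-drink deletion lowers AUC(0-24) by 24% (2.91 to 2.22) at an LLOQ of 5% of placebo peak and by 39% (2.91 to 1.78) at 10%. These figures rest on invented levels, decline rates and sampling times. The change is worth making because it is cheap and removes a treatment-dependent analysis rule from the main PD measure, not because a bias has been demonstrated.

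**What to change.** Add to SAP 9.3 and 9.4.3, for fructose only:

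- BQL values are set to LLOQ/2 in all four AUCs and in the mean profiles.
- A sensitivity analysis sets them to zero, with the linear trapezoid on the affected segments because the log rule needs positive values.
- The profile-termination rule does not apply to the fructose tolerance test.
- The fructose LLOQ is stated, and BQL counts are tabulated by treatment and time point.

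The cost is a few sentences, one table and one rerun. If no BQL values occur, no result changes. The downside is that LLOQ/2 is approximate when the LLOQ is high relative to the placebo peak; the counts and the zero-substitution run show the reader when that applies.
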